## 7. Abstract Summary:

It has been demonstrated that infants in developing countries, have lower immune responses to vaccines such as rotavirus vaccine and oral polio vaccine, compared to the responses of infants from developed countries. One explanation may be malnutrition. Several micronutrients are known to affect the immune system in characteristic ways; of which vitamin A and zinc exert the most significant effects. In the proposed study we would like to evaluate the humoral and cell mediated immune responses of infants supplemented with zinc from birth until six months of age and of children born to mothers supplemented with zinc during the last five months of their pregnancy.

Pregnant women at 12-16 weeks of pregnancy were randomized to one of 2 groups (A or B). Group A women has been supplemented daily with tablets of 30 mg (2 x RDA) of zinc (as acetate) until delivery and group B women received a placebo. Infants less than four weeks of age, born to a separate cohort of mothers who were not involved in the pregnancy zinc supplementation study, will be randomized to one of two groups (C or D). Group C infants will be supplemented daily with 10 mg of elemental zinc until six months of age and group D infants will receive a placebo. Infants born to women who were supplemented with zinc or placebo (groups A & B), and groups (C & D) infants will receive the routine childhood immunization as recommended by the Expanded Program on Immunization (EPI). In addition they will receive three doses of the combined diphtheria, tetanus toxoid, and pertussis (DTP)-Haemophilus Influenza type B (Hib) vaccine (Diphtheria CRM197 Protein Conjugate) TETRAMUNE (Lederle-Praxis), at four weeks intervals beginning at six weeks of age. Blood samples will be obtained at 6 and 24 weeks of age. The sera obtained at six and 24 weeks will be assayed for antibodies to DTP-Hib vaccine serotypes, and to all three serotypes of the trivalent oral polio vaccine (TOPV). Tuberculin testing will be performed with purified protein derivative (PPD) at 24 weeks of age as a measure for cell mediated immune response to BCG.

## A. INTRODUCTION

### 1. Objectives

1. To evaluate the effect of zinc supplementation of mothers during pregnancy on infants immune responses to the Haemophilus Influenza type b, oral polio, and BCG vaccines.
2. To evaluate the effect of zinc supplementation of infants beginning at 4 weeks of age on their immune responses to the Haemophilus Influenza type b, oral polio, and BCG vaccines.

### 2. Background:

The responses to childhood vaccinations especially to certain antigens are known to vary in different populations. In many developing countries, the immunogenicity of three doses of live attenuated, trivalent oral polio vaccine (TOPV) is lower than industrialized countries. Whereas, rates of sero-conversion following the administration of TOPV approach 100% in industrialized countries, only 73% (range, 36%-99%) and 70% (range, 40%-99%) of children in developing countries have detectable antibody level to poliovirus type 1 and 3 respectively after receiving three doses of TOPV. Recently, a study conducted in Bangladesh strongly suggests that concurrent diarrheal illness contributes to the less than optimal humoral immune response to TOPV. Similarly, the immune responses to Haemophilus influenzae type b (Hib) vaccines of some populations such as, certain American Indian populations are known to be lower than the general U.S. population, and the immune responses to rotavirus vaccines are known to be lower in infants from developing countries compared to infants from developed countries.

There may be various reasons for the depressed immune responses to vaccines among infants in developing countries. One explanation may be malnutrition. Undernourished infants are known to have depressed immune responses. Several micronutrients are known to affect the immune system in characteristic ways, vitamin A and zinc exert the most significant effects.

The zinc atom has a unique combination of physical and chemical properties that render it useful in biological systems. Zinc appears to have distinct roles in the mammalian metabolism and being a component of zinc-containing metalloenzymes, zinc is important for nearly all aspects of cellular metabolism^9.

*Zinc and immunity:* The following evidence suggests that zinc plays an important role in immunity, zinc deficiency: (i) impairs cell regeneration (due to its role in metalloenzymes, and other metabolic pathways); (ii) impairs immunocompetence with reduced cell mediated immune response, decreased T-lymphocytes, and abnormal T- Helper and/or suppressor cell functions, (iii) impairs macrophage function thus depressing the delayed hypersensitivity reaction; (iv) reduces the natural killer cells and antibody dependent cytotoxicity, (v) impairs epithelial barrier functions, (both skin lesions and mucosal defects are common findings); and (vi) impairs linear growth. Zinc supplementation has been shown to improve growth, indeed poor growth and diarrhea are cardinal features of acrodermatitis enteropathica, the phenotypic expression of which is attributable to severe zinc deficiency.

Several studies have demonstrated a reduction in infant morbidity due to infections in response to dietary zinc supplementation. Schlesinger et al. observed that zinc fortified formula improved linear growth and immune response in 7 month old Chilean infants. In a study among preschool children in rural Mexico, supplementation with 20 mg zinc/day for 12 months reduced the number of episodes of diarrhea and respiratory diseases. Recently, Sazawal et al., demonstrated that dietary supplements of zinc along with selected vitamins, resulted in clinically important reductions in the duration and severity of diarrhea among preschool-age children. In rural Bangladesh, normal fullterm infants showed significantly better growth and less diarrheal morbidity after zinc supplementation.

Furthermore, there are obvious interactions between zinc and vitamin A deficiency. For instance, zinc deficiency decreases the rate of production of retinol-binding protein. It may also hinder absorption of vitamin A.

### **3. Rationale**

In the proposed study we would like to evaluate the effect of zinc supplementation of mothers during the last five months of pregnancy and the effect of zinc supplementation during the first six months of life on the humoral seroresponses of infants, using Hib and TOPV vaccines as markers. The cell mediated immune response will be evaluated using PPD skin reaction to BCG as a marker.

### **B. SPECIFIC AIMS**

#### **Hypothesis**

Zinc supplementation of infants beginning at 4 weeks of age, or zinc supplementation during the last five months of pregnancy will enhance infants immune responses to Haemophilus influenzae type B, oral polio, and BCG vaccines.

### **C. METHODS OF PROCEDURE**

#### **Study design**

A prospective, four cell, double-blind design is proposed. Women (between 12 and 16 weeks gestation) and infants (less than 4 weeks old) will be enrolled and assigned to one of two groups, zinc or placebo. Pregnant women were randomized to groups (A or B). Group A women were supplemented daily with tablets of 30 mg of zinc (2 x RDA), as acetate, until delivery, and group B women received a placebo. Infants born to mothers in group A and B will be prospectively followed without additional zinc supplementation and their responses to various immunization will be evaluated. A separate cohort of infants will be enrolled at birth and randomized to receive 10 mg (2 x RDA) of zinc or a placebo (group C and group D) beginning at 4 weeks of age. Infants in groups C and D will also have their responses to various immunization evaluated.

## **Inclusion Criteria**

### **Pregnant Women**

All pregnant women, living in the study area (see section V) in Dhaka, Bangladesh were eligible for the study provided they met the following criteria:

1. Were identified by the surveillance system of the International Center for Diarrheal Diseases, Bangladesh (ICDDR,B)
2. Met the criteria of residence
3. Were 12-16 weeks of gestation
4. Agreed to participate
5. Remained at/near Dhaka for the delivery
6. Gave a written informed consent.

### **Infants**

Infants, living in the study area will be eligible for the study provided they meet the following criteria:

1. Age less than 4 weeks
2. In good general health without known underlying illness.
3. Parents give written informed consent.

## **Exclusion Criteria**

Pregnant women with abnormal pregnancies or other significant illness were excluded from the study.

Infants will be excluded if they have one or more of the following:

1. Known or suspected hypersensitivity to one of the vaccine antigens or components
2. Presence of immune system disorder
3. Recipients of immunosuppressive therapy, blood products, corticosteroids or immunoglobulin
4. History of prior vaccination with OPV and/or DPT vaccine
5. Previous invasive Haemophilus Influenza disease (in the first 15 days of age)
6. Acute febrile illness (temperature  $>38.1^{\circ}\text{C}$ ) within 72 hours.
7. Major congenital malformation or serious chronic illness.

8. Subject involved in any other vaccine trial.

### Randomization

This will be a four cell double blind controlled safety and immunogenicity trial (table 1). Pregnant women at 12-16 weeks of pregnancy, who meet the inclusion criteria, were randomized to one of 2 groups (A or B). Group A women was supplemented daily with tablets of 30 mg of zinc (zinc acetate) until delivery. The amount of 30 mg of zinc/day is twice the RDA for zinc during pregnancy and there is no evidence of adverse effects for either the mother or fetus. Previous investigators have used daily oral dose of up to 30mg with no adverse effects. Zinc acetate has been used because salts of zinc acetate generally result in less nausea and gastrointestinal irritation than other zinc salts. Group B women received a placebo, containing an inert substance (sucrose, maize starch, cellulose). A separate cohort of infants less than four weeks of age, whose mothers did not participate in the zinc trial and who meet the inclusion criteria, will be randomized to one of 2 groups (C or D). Group C infants will be supplemented daily with 10 mg of elemental zinc which is twice the RDA, until 6 months of age. Group D infants will receive a placebo. The zinc supplement and the placebo will be indistinguishable in appearance and taste.

Table 1		
STUDY SCHEMA		
Group	Pregnancy*	Infancy#
A	Zinc	-
B	Placebo	-
C	-	Zinc
D	-	Placebo

\*From 12-16 weeks of gestation until delivery

#From 4 weeks of age until 6 months of age

## **Data Collection**

Women have been recruited through the identification system (described in section V) before 16 weeks of pregnancy and written informed consent has been obtained. At 16 weeks gestation, a standard questionnaire has been administered to the women. Women were randomly assigned to one of the two treatment groups (A or B), and supplementation begun at 16 weeks gestation until delivery. Health workers delivered a one week supply of the zinc supplement or placebo tablets at the houses weekly. They instructed pregnant women to consume the tablets preferably together with a meal or a drink and not together with other vitamins/mineral. Compliance has been checked by counting the remaining tablets at the following visit.

The zinc and placebo preparations for infants will look identical and will be dispensed in bottles in the liquid form. A one week supply of zinc or placebo will be delivered to the home once a week. Each dose will be dispensed in a separate vial. Compliance will be checked by measuring the remaining amount of liquid in the bottles.

Any vomiting or diarrhea that occurs in the pregnant women or infants will be recorded. Anthropometrics (weight, length, midupper arm circumference, head circumference, chest circumference) will be measured at monthly intervals.

## **Immunization and Serology**

Infants born to women who were supplemented with zinc or placebo (groups A & B), and supplemented infants groups (C & D) will receive three doses of the combined diphtheria, tetanus toxoid and pertussis (DTP)- Haemophilus Influenza type b (Hib) vaccine (Diphtheria CRM, 97 protein conjugate) Tetramune, (Lederle- Praxis) at 6,10, and 14 weeks of age, at the same time as trivalent oral polio vaccine (TOPV). The BCG vaccine will be administered at birth.

Table 2						
Schedule for Immunization and Testing						
Age (weeks)	Birth	4 weeks	6 weeks	10 weeks	14 weeks	24 weeks
BCG	X					
TOPV			X	X	X	
DPT-Hib			X	X	X	
Blood testing*		X				X
Skin test						X

TOPV = Trivalent Oral polio vaccine, DPT-Hib = Diphtheria, pertussis and tetanus-Haemophilus Influenza type b vaccine, BCG = Bacillus Calmette-Guerin, Skin test = Mantoux test 5 TU-PPD.

\*At 4 weeks of age, a base-line blood specimen for plasma zinc and pre-vaccination DPT-Hib & polio serologies and at 24 weeks of age, post-vaccination DPT-Hib, polio serologies and plasma zinc.

Blood specimens (2.5ml of whole venous blood) will be obtained from all infants, at 4 weeks (baseline), and 24 weeks (10 weeks after third doses of pneumococcal and polio vaccines) The pre-vaccination specimen will be obtained at 4 weeks instead of 6 weeks of age since a blood sample is obtained at 4 weeks of age as part of the ongoing study. Sera will be assayed for antibodies to H. influenza b polysaccharide and TOPV (all three serotypes).

Cell-mediated immune response of each infant will be determined by tuberculin testing with purified protein derivative (PPD) at 6 months of age. Tuberculin testing and reading will be performed by trained health workers. They will apply tuberculin solution (PPD) (0.1ml) to the volar surface of the forearm using an Omega glass PPD syringe with platinum needles. After 72 hours the size will be read in millimeters as the transverse diameter of induration developed. An induration > 2mm will be considered positive. Health workers will be extensively trained and standardized in the administration and interpretation of PPD skin testing.

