## ANNEX

### TIME FRAME OF THE STUDY

January 1997	- Procuring supplies recruiting and training study personnel
February 1977 - October 1997	- Enrollment, data collection, and laboratory studies.
November 1997- December 1997	- Completion of collection and processing serum samples
January 1998- December 1998	- Laboratory studies, data analysis and publication.

**Summary of protocol and progress of the ongoing study:  
Effect of zinc supplementation during pregnancy on infant  
birth weight, growth, morbidity and response to BCG.**

Investigators: [name], Dr. [name], Dr. [name], [name] [name],  
Mr. [name], Dr. [name]  
International Centre for Diarrhoeal Disease Research, Bangladesh  
(ICDDR,B); Department of Human Nutrition, Wageningen  
Agricultural University, The Netherlands

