### **Current status**

After a delay in activities in the month of February 1996 due to external causes (political unrest, elections) data collection actually started from March 1, 1996. Enrollment of women was slowed down in March because of political actions but as soon as the situation went back to normal (by April 1, 1996) we were able to catch up and completed enrollment by the end of June 1996. By the end of June, a total of 559 pregnant women had entered the study. Data collection is expected to be completed by the end of June 1997.

To date, 401 women delivered, including 378 live births, 12 still births and 11 early neonatal deaths (within 7 days after birth). So far, the birth notification system has been very efficient: 371 infants were visited within 72 hours. For 114 (31%) of these infants birth weights were measured on the day of delivery. In 6 cases birth weight assessments exceeded 72 hours due to late notification (n=3) and delivering outside Dhaka (n=3). Forty three women remain pregnant in the follow-up and are expected to deliver in the next month. By the end of December 1996, the first infant will reach the age of six months and will be released from the study.

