### **Significance**

As far as we are aware, this study would be one of the first zinc supplementation trials among pregnant women in a very poor urban community with a high prevalence of low birth weight. Information obtained from the study will increase the understanding of the importance of zinc supplementation during pregnancy on infant birth weight, growth, immune response and morbidity in urban populations in developing countries.

Information derived from this study will be essential for planning and implementing health intervention programs aimed at reducing the incidence of low birth weight, improving maternal health, and improving infant growth and immunity. The information can also be used to make existing programs more cost-efficient.

December 9, 1996

**INTERNATIONAL CENTRE FOR DIARRHOEAL DISEASE  
RESEARCH, BANGLADESH (ICDDR,B)**

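### On the annex's own dates, groups A and B cannot supply about 122 infants each given study DPT-Hib at 6, 10 and 14 weeks and bled 10 weeks after dose 3

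*Protocol*

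**What the plan says.** Immunization and Serology gives study DPT-Hib to all four groups "at 6,10, and 14 weeks of age, at the same time as trivalent oral polio vaccine (TOPV". It sets the second blood sample at 24 weeks, described as 10 weeks after the third dose (the text prints pneumococcal there; I read it as Hib). Sample Size plans about 122 infants per group, and the PRP row of Table 3 enrols 113. Objective 1 names Hib first among the three vaccines for the maternal-zinc comparison.

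The annex supplies the calendar. Under Time Frame of the Study, January 1997 is for "Procuring supplies recruiting and training study personnel", and February to October 1997 is for "Enrollment, data collection, and laboratory studies" (the start year is printed 1977, evidently 1997). Under Current Status, in a summary that closes with the date "December 9, 1996", the pregnancy trial had "completed enrollment by the end of June 1996". At that point "401 women delivered, including 378 live births", and "Forty three women remain pregnant in the follow-up and are expected to deliver in the next month". The summary adds: "By the end of December 1996, the first infant will reach the age of six months and will be released from the study".

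**The concern.** Groups A and B are a closed cohort that was nearly all born before this project's first working month. An infant can receive a first dose at 6 weeks only if vaccine is available when the infant reaches that age. If vaccine arrives in February 1997, most A/B infants are already too old for the stated ages, and no later births can be added.

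At stake is the Hib part of Objective 1. The PRP assumption in Sample Size is stated for infants who complete the three-dose course. As dated, the A versus B comparison cannot be made in the stated number of infants on the stated schedule. Infants vaccinated late would be bled at a different interval after dose 3 from the one the Protocol describes. Groups C and D are enrolled during 1997 and are not affected.

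**Working it through.** **The plan's own number.** For 70% versus 50% anergic, two-sided 5%, 80% power: [1.96√(2×0.6×0.4) + 0.8416√(0.7×0.3 + 0.5×0.5)]² / 0.2² = 93. With continuity correction this is 103. Then 103/0.85 = 121.2, so 122 per group and 2 × 122 = 244 for A and B. The stated size reproduces.

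**Inputs from Current Status.** On 9 December 1996 there had been 401 deliveries = 378 live births + 12 stillbirths + 11 early neonatal deaths, with 43 pregnancies open and due within a month. Scaling by 378/401, the 43 pregnancies yield 43 × 378/401 = 40.5 live infants.

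**Strict schedule, vaccine from 1 February 1997 (assumed).**
- The earliest usable birth date is 1 February − 42 days = 21 December 1996.
- The youngest of the 378 reaches 6 weeks by 9 December + 42 days = 20 January 1997, and on 1 February is 54 days (7.7 weeks) old. None of the 378 qualifies.
- If all 43 remaining births fall on or after 21 December: 40.5 live infants.
- If they are spread evenly over the 31 days from 9 December, 19 of those days count: 43 × 19/31 = 26.4 deliveries, and 26.4 × 378/401 = 24.8 live infants.
- Result: about 25 to 41 of 244 (10% to 17%). After 15% attrition: 21.1 to 34.5 in total, or 10.6 to 17.2 per group.

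**Other start dates and age limits.** The Protocol does not give the distribution of birth dates. I spread the 378 live births evenly up to 9 December from three assumed first dates: 30 June (162 days, 2.33 per day), 16 August (115 days, 3.29 per day) and 1 September (99 days, 3.82 per day). Live infants = 40.5 + daily rate × qualifying days before 9 December.

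| Vaccine from | Oldest age at dose 1 | Born on or after | Qualifying days before 9 Dec | Live A/B infants (three spreads) |
|---|---|---|---|---|
| 1 Feb 1997 | 12 weeks | 9 Nov 1996 | 30 | 110, 139, 155 |
| 1 Jan 1997 | 6 weeks | 20 Nov 1996 | 19 | 85, 103, 113 |
| 1 Jan 1997 | 12 weeks | 9 Oct 1996 | 61 | 183, 241, 273 |

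**Start date needed for 244 on the strict schedule.** 244 − 40.5 = 203.5 of the 378 would have to qualify. Under the three spreads, vaccine would have to be in use by 25 October, 20 November or 28 November 1996. All three fall before the 9 December summary and before the January procurement.

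**Interval to the 24-week bleed when doses are late but four weeks apart.**
- Youngest of the 378, 1 February start: dose 3 at 7.7 + 8 = 15.7 weeks, so 24 − 15.7 = 8.3 weeks.
- First dose at 12 weeks: dose 3 at 20 weeks, so 4 weeks.
- Older than 16 weeks on 1 February (born before 12 October 1996): no third dose by 24 weeks.

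**Power.** Sample Size puts the control rate at 30%, described as 20% below the U.S. rate, which implies a target of 50%. Table 3 prints 98%. For 30% versus 50%, the pair that also gives the printed 103, power at 13 to 21 per group (26/2 to 43/2, before deaths and attrition) is about 17% to 26%. For 30% versus 98%, 7 per group suffice (10 with continuity correction), and power at 13 per group is 99%.

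**The case against.** The strongest reply is that 1 February is my date, not the Protocol's. The time frame is by month and covers the whole project. Its enrolment entry can only mean groups C and D, because A/B enrolment was over. A/B infants were already being visited in the ongoing study, and the supplies budget has no vaccine line, so January procurement is not shown to mean vaccine. All of this stands, and it is why the result is a range. It does not rescue the plan, however. No section says A/B infants had started study vaccine, the schedule is written in the future tense, and the summary of the ongoing study mentions neither DPT-Hib nor Hib serology.

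Second, the Protocol gives target ages and no windows, and the Abstract Summary speaks of four-week intervals from six weeks. Late first doses are not forbidden. This also stands: a 1 January start with first doses up to 12 weeks could come close to 244 or pass it (183 to 273). That takes both an earlier start than the time frame shows and a window the Protocol does not state, and it gives up the 10-week interval. With a 1 February start the same window still falls well short.

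A reader might infer that the A versus B comparison would be biased. The documents do not support that. Mothers were randomised, so calendar-driven lateness falls on both groups alike; it adds noise and changes the interval being studied.

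A reader might also infer that the Hib comparison is underpowered, or that Hib must leave Objective 1. Neither follows. Power is lost under 30% versus 50% but not under the printed 30% versus 98%, and a smaller, clearly defined randomised comparison is still worth having.

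**Conclusion.** The schedule, the planned number and the calendar do not fit together for Hib in groups A and B. With vaccine from 1 February 1997, about 25 to 41 live infants can follow the stated schedule, against 244 planned. With first doses allowed up to 12 weeks, it is about 110 to 155, bled between 10 and 4 weeks after dose 3. With vaccine from 1 January 1997, about 85 to 113 can follow it strictly.

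These figures assume that 1977 means 1997, that the remaining 43 pregnancies end as the first 401 did, and that earlier births were spread evenly from one of the three dates used. They count infants who could start on time, before the 15% attrition except where shown.

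The 25 to 41 should not be read as the number able to give any Hib data; it is the number on the exact stated ages. PPD in A/B is unaffected. A/B polio is not challenged on these dates, but it cannot be assumed to keep its full number. Exclusion Criteria rule out infants with earlier OPV or DPT, and the immunization form has codes for both vaccines given through EPI. How that exclusion applies to A/B is not said.

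**What to change.** In Immunization and Serology, state the first study-vaccination date for groups A and B and the oldest age allowed at first dose. In Sample Size and the PRP row of Table 3, replace 113/122 for A/B with the number that this date and window can deliver, and let the full Hib number apply to C and D only. Define the A/B Hib comparison as that subset, and record age at first dose and the interval from dose 3 to the bleed. If study vaccine was already in use in the ongoing study, give the date it began.

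In Exclusion Criteria, state how the prior OPV/DPT rule applies to A/B infants already vaccinated through EPI, for both Hib and polio. PPD needs no change.

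This is a text change, apart from recording two items that follow from the dose and sampling dates; it adds no visits or samples. The cost is that the A/B Hib result will be less precise than the Protocol now implies.
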